14.2.3 Overall Survival

Overall survival (OS) time is defined as the time (in months) from the first administration of study treatment to the date of death.

For participants not known to be deceased at time of analysis or who died after the cut-off date, OS time will be censored at the date of last contact before data cut-off date as defined in Section 9.66.

The Kaplan-Meier based analysis described in Section 14.2.2 for the derivation of progression-free related estimates will be repeated for the survival related estimates.

The censoring and event status with respect to OS will be summarized

Estimand Attributes

Endpoint:

- OS as measured by time from first dose to death

Population:

- Participants with *RAS/BRAF* wild-type left-sided metastatic colorectal cancer (mCRC) having acquired resistance to anti-EGFR antibody targeting therapy due to *MET* amplification

Treatment:

- Tepotinib combined with cetuximab

Intercurrent Event Strategy:

- Discontinuation of treatment (treatment-policy strategy, i.e. regardless of the intercurrent event)
- Start of subsequent anti-cancer treatment (treatment-policy strategy, i.e. regardless of the intercurrent event)

Population Level Summary:

- Kaplan-Meier estimates

Follow-Up Duration of OS

In order to assess the follow-up duration of OS, Kaplan Meier estimates will be calculated reversing the OS censoring and event indicators.

Kaplan-Meier estimates (product-limit estimates) will be presented in the same way as in the analysis described above for OS.

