## Follow-up Period

All participants are to be followed up after stop of treatment with tepotinib and cetuximab, including an End of Treatment (EoT) Visit within 14 days of the last dose of tepotinib and/or cetuximab. A Safety Follow-up Visit will occur 30 (- 3 to + 7) days after the last dose of tepotinib and/or cetuximab for all participants who discontinued the study intervention permanently. After the Safety Follow-up Visit, the Survival Follow-up is to be performed every 3 months ( $\pm$ 1 month) at clinic visits or by telephone contact for up to 1 year. Participants' survival information will be collected. Any subsequent anticancer therapy given to the participant until death should be recorded.

Participants who discontinue treatment for reasons other than progressive disease (PD) or death will have additional visits for tumor assessments every 6 weeks until 9 months and every 12 weeks thereafter until disease progression, death, or withdrawal of consent. A  $\pm$  7-day time window is permitted for these additional follow-up visits until 9 months, and  $\pm$  14 days thereafter.

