OS (months) assessed by the Investigators	
Overall survival is defined as the time (in months) from first administration of study intervention to the date of death. For participants not known to be deceased at time of analysis, OS time will be censored at the last date the participant was known to be alive. If this date is after the data cutoff, participants will be censored at the date of data cutoff.
 
Overall survival will be summarized descriptively. Kaplan-Meier plots as well as the corresponding number of events, first and third quartile (Q1 and Q3), median, minimum and maximum from the Kaplan-Meier product-limit estimates of the survival function and survival rates at 3, 6, 9, 12, 15, and 18 months together with corresponding 95% CI will be presented.

CCI

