9.1 Data Handling After Cut-off Date

By its nature, data after cut-off may be incomplete and subject to further change and will not be used for summary statistics, statistical analyses, listings or imputations.

Stop dates are not affected by this rule, e.g. a stop date of AEs, which starts prior to the cut-off, but stops after date of cut-off, will not be changed.

These rules will be applied to all analyses performed for the interim analysis for futility and main analysis. For the final analysis no cut-off date will be applied: the analysis will be performed only after all the data have been collected, fully cleaned and the database has been locked.

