9.6 Date of last Contact

The date of last contact will be derived for participants not known to have died at the analysis cut-off using the latest complete date prior to or at the data cut-off date among the following:

- All participant assessment dates (blood draws (laboratory, PK), vital signs, performance status, ECG, tumor assessments, quality of life assessments)
- Start and end dates of anti-cancer therapies administered after study treatment discontinuation.
- AE start and end dates
- Concomitant medication/procedures start and end dates
- Last known to be alive date collected on the ‘Survival Follow-up’ eCRF
- Tepotinib and cetuximab administration start and end dates
- Date of discontinuation on disposition eCRF pages (do not use if reason for discontinuation is lost to follow-up)

Only dates associated with actual examinations of the participant reported in the eCRF will be used in the derivation. Dates associated with a technical operation unrelated to participant status such as the date a blood sample was processed will not be used. Assessment dates after the cut-off date will not be applied to derive the last contact date. This rule is to be applied to AE stop dates, too: if an AE started before the cut-off date and ended after the cut-off date, only the complete start date will be used in the derivation of the last date of contact.

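### The SAP censors OS at the last contact before the data cut-off where the protocol censors at the cut-off itself, which lowers primary-analysis OS whenever the database holds post-cut-off information

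*SAP*

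**What the plan says.** Protocol 9.4.1 gives the OS rule in two steps. For participants not known to be deceased, "OS time will be censored at the last date the participant was known to be alive". It then adds: "If this date is after the data cutoff, participants will be censored at the date of data cutoff".

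SAP 14.2.3 covers a wider group, "For participants not known to be deceased at time of analysis or who died after the cut-off date", and for all of them "OS time will be censored at the date of last contact before data cut-off date". SAP 9.6 defines that date "using the latest complete date prior to or at the data cut-off date among the following" and adds: "Assessment dates after the cut-off date will not be applied to derive the last contact date". SAP 9.1 sets the general principle for analyses with a cut-off: data after it "will not be used for summary statistics, statistical analyses, listings or imputations".

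Off treatment, Protocol 4.1 (Follow-up Period) says "the Survival Follow-up is to be performed every 3 months", with a window of 1 month either way, for up to 1 year. SAP 6.3 places the primary analysis about 5 months after the last participant's first dose. SAP Section 7, which should list departures from the protocol's analyses, covers only COVID-19. The SAP says it is based on protocol version 1.0, but the version 2.0 change log reports changes to DoR and PFS in 9.4.1 and none to OS, so the version gap does not explain the difference.

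**The concern.** A participant seen alive after the cut-off, or who died after it, was alive on the cut-off date. The protocol uses that fact; the SAP discards it. The SAP identifies participants who died after the cut-off and then censors them at a date before it.

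The effect is one-sided. A death in the interval between last contact and cut-off counts as an event. A survivor of the same interval contributes no time at risk there. This inflates the hazard near the end of each participant's follow-up and pulls down the Kaplan-Meier curve. The estimates at stake are median OS and the landmark OS rates at the primary analysis, the OS subgroup estimates (SAP 14.2.5), and the reverse Kaplan-Meier follow-up for OS (SAP 14.2.3), which is understated because it uses the same early dates.

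**Working it through.** **The two rules as formulas.** On a participant's own clock, let C be the cut-off and L the last contact on or before C.

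- Death on or before C: event at the death date under both rules.
- Alive at C, with a contact or death known after C: protocol censors at C, SAP at L. Time lost is C − L.
- Alive at C as far as known, nothing known after C: both rules censor at L.

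**How large C − L can be.** On treatment, visits are weekly, so the loss is days. In survival follow-up, contacts are 3 months apart, or up to 3 + 1 + 1 = 5 months if one is early and the next late.

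**Is there a plan figure to reproduce?** No. The documents state no OS assumption or OS figure, so every size below rests on assumptions.

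**Simulation 1 (n = 22, Cohort A's size).** Exponential OS with medians taken from studies cited in Protocol 2.2 (9.2, 13.8 and 19.8 months). Exponential time on treatment with median 5 × 21 / 30.4375 = 3.45 months, from the protocol's 5-cycle planning figure. Uniform accrual. Cut-off 5 months after the last first dose. Weekly contacts on treatment, a 30-day visit, then four contacts 3 months apart with ±1 month jitter. All deaths up to the cut-off are counted. Any later contact, or a death within 3 months after the cut-off, counts as post-cut-off information, so this is a generous setting for such information.

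| Median OS (months) | Accrual (months) | 12-month OS, protocol | 12-month OS, SAP | Difference (points) | Typical KM median, protocol / SAP (months) |
|---|---|---|---|---|---|
| 9.2 | 12 | 0.405 | 0.358 | 4.7 | 9.11 / 8.58 |
| 9.2 | 24 | 0.410 | 0.394 | 1.6 | 9.42 / 9.09 |
| 13.8 | 12 | 0.549 | 0.509 | 4.0 | 14.35 / 12.42 |
| 13.8 | 24 | 0.551 | 0.537 | 1.4 | 13.78 / 13.16 |
| 19.8 | 12 | 0.656 | 0.616 | 4.0 | not reached |
| 19.8 | 24 | 0.658 | 0.645 | 1.3 | 18.26 / 17.38 |

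- The exact 12-month value for median 9.2 is 0.5^(12/9.2) = 0.405, which the protocol rule recovers with 12-month accrual.
- Mean C − L among survivors with later information was about 1.1 to 1.5 months, with a 90th percentile of about 2.7 to 3.1 months.
- With 6-month accrual the longest possible follow-up is 6 + 5 = 11 months, so no 12-month estimate is meaningful. At 9 months the values were 0.508 and 0.433, a gap of 7.5 points (median OS 9.2).
- With n = 1000, median 9.2 and 12-month accrual, the values were 0.411 and 0.371. The gap of 4.0 points is therefore bias, not small-sample noise.

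**Simulation 2 (large sample, limited snapshot delay).** Median OS 9.2 or 12 months; accrual 12 or 18 months.

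- Snapshot at the cut-off: identical results under both rules.
- Snapshot 1 to 3 months later: the SAP rule gives 12-month OS about 1.1 to 4.4 points, and median OS about 0.2 to 1.1 months, below the protocol rule, which stays near the truth.

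**Against sampling error.** With complete follow-up, the standard error of a 12-month rate of 0.405 in 22 participants is √(0.405 × 0.595 / 22) = 0.105, or about 10.5 points. With censoring (median 9.2, 18-month accrual, 2-month snapshot delay) the simulated SD was about 12 points, against a mean difference between rules of about 2 points.

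**The case against.** The SAP has a stated reason. SAP 9.1 treats post-cut-off data as possibly incomplete and changeable, and 9.6 and 14.2.3 apply that consistently. This stands as an argument about what else must be amended, but it does not rescue the rule. An alive-on-cut-off flag needs only the existence of a later contact or death, and 9.1 already makes an exception for stop dates.

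The bias is conditional. The documents do not give the delay between cut-off and snapshot, nor how deaths become known. With no delay, both rules are near the truth if deaths are learned at the next contact; if deaths are learned at once, both are low by about 2 to 5 points and restoring the protocol rule changes nothing. This stands. However, 14.2.3 itself provides for participants known to have died after the cut-off, so the SAP expects such information to be present.

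No sentence says outright that a death dated before the cut-off but learned later is counted. The wording of 14.2.3, which refers to what is known at the time of analysis, supports that reading. The opening of 9.6, which refers to the cut-off, is less clear.

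The simulations leave out contact sources that SAP 9.6 counts: 6-weekly tumour visits for those who stop without progression, and dates of AEs, concomitant medication and subsequent therapy. These would shorten C − L and shrink the difference. This also stands.

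**Conclusion.** The protocol and SAP rules conflict, and the departure is undeclared. That part needs no assumption. The downward bias in primary-analysis OS follows only when post-cut-off information is in the database. Under the second simulation's assumptions its size is about 1 to 4.5 points at 12 months and 0.2 to 1.1 months in the median, rule against rule, and probably less once the omitted contact sources are included. Faster accrual or longer survival can widen it, as the first simulation shows.

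A reader might infer that OS in this trial is understated in every case, or that survivors generally lose months of follow-up. The documents do not support either: without later information the rules give the same date, and participants still on treatment lose days. Nor does the point reach the trial's main conclusions. OS is secondary and descriptive, the final analysis applies no cut-off, and the response rate, sample size and futility rule do not use OS censoring. It remains a systematic error in a reported estimate, and cheap to remove.

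**What to change.** - **SAP 14.2.3 and 9.6:** censor at the cut-off date any participant with a contact or death dated after the cut-off; censor all other participants without an OS event at last contact.
- **SAP 9.1:** add an explicit exception allowing post-cut-off data for this alive-on-cut-off flag and for nothing else. Without it the corrected rule would contradict 9.1.
- **SAP 14.2.3:** correct the cross-reference from Section 9.66 to 9.6.

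If the sponsor prefers to keep the present rule, it should be declared and justified in SAP Section 7. The preferred change costs a few lines of SAP text and minor programming, and needs no new data.

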14.2.4 Immunogenicity

Immunogenicity of cetuximab will be measured by ADA assays at Baseline on Day 1 Cycle 1 and End of Treatment Visit.

Immunogenicity of cetuximab will be tabulated by cohort and dose level, if applicable, based on Immunogenicity Analysis Set. The immunogenicity status of each study participant will be evaluated according to the criteria described in [Table 5](#).

Table 5 **Immunogenicity classification**

ADA result at Baseline	ADA result at EOT	Classification
Negative	Negative	Treatment-emergent negative
Negative	Positive	Treatment-emergent positive
Positive	Negative, or positive with titer lower or equal to baseline	Treatment-emergent negative
Positive	Positive with titer higher than baseline	Treatment-emergent positive
Missing	Negative or positive	Not evaluable
Negative or positive	Missing	Not evaluable
Missing	Missing	Not evaluable

Immunogenicity of cetuximab will be listed.

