Activity / Assessment	Screening / Baseline	Intervention Period (in cycles of 3 weeks)									EoT	Safety Follow up / Discontinuation	Survival Follow-Up / EoS / 1-Year Follow-Up	Notes
	Day -56 to Day -1	Cycle 1 (21 days)		Cycle 2 (21 days)		Cycle 3 and subsequent cycles (21 days)					Within 14 days after decision to withdraw IMP	30 days after the last dose	After Safety Follow-Up, every 3 months, up to 1-year Site Visit or by Telephone	
Cycle Day		1	8	15	1	8	15	1	8	15				
Visit Window		± 3 days		± 3 days		± 3 days						- 3 to + 7 days	± 1 month	
AE and SAE assessment	X	Continuous											From the time of signing the ICF through Safety Follow-up Visit.	
Concomitant medication and procedures review	X	Continuous											Procedures review includes the capture of cytology results.	
Blood hematology, biochemistry	X	X	X	X	X	X	X	X	X	X			Including thrombocytes, after Cycle ≥ 2 only D1. Serum cystatin C (only for sites where the test is available).	
Urinalysis	X	X	X		X		X		X	X				
Coagulation (PT, aPTT, INR)	X	X	X		X		X		X	X				
CCI														

Activity / Assessment	Screening / Baseline	Intervention Period (in cycles of 3 weeks)									EoT	Safety Follow up / Discontinuation	Survival Follow-Up / EoS / 1-Year Follow-Up	Notes
	Day -56 to Day -1	Cycle 1 (21 days)		Cycle 2 (21 days)		Cycle 3 and subsequent cycles (21 days)					Within 14 days after decision to withdraw IMP	30 days after the last dose	After Safety Follow-Up, every 3 months, up to 1-year Site Visit or by Telephone	
Cycle Day		1	8	15	1	8	15	1	8	15				
Visit Window		± 3 days		± 3 days		± 3 days						- 3 to + 7 days	± 1 month	
														CCI

CCI

Activity / Assessment	Screening / Baseline	Intervention Period (in cycles of 3 weeks)									EoT	Safety Follow up / Discontinuation	Survival Follow-Up / EoS / 1-Year Follow-Up	Notes
	Day -56 to Day -1	Cycle 1 (21 days)		Cycle 2 (21 days)		Cycle 3 and subsequent cycles (21 days)					Within 14 days after decision to withdraw IMP	30 days after the last dose	After Safety Follow-Up, every 3 months, up to 1-year Site Visit or by Telephone	
Cycle Day		1	8	15	1	8	15	1	8	15				
Visit Window			± 3 days		± 3 days		± 3 days					- 3 to + 7 days	± 1 month	
ADA cetuximab		X									X			Serum ADA samples will be collected predose (within 60 min before tepotinib dose) only on Cycle 1 Day 1 and at EoT (See Appendix 4 ) and Section 8.9.
CCI														

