#### Type of Participant and Disease Characteristics

2. Advanced (locally advanced or metastatic, unresectable) left-sided (from splenic flexure to rectum – National Comprehensive Cancer Network CRC Version 1.2021 guidelines) CRC with *RAS/BRAF* wild-type at study entry confirmed prior to enrollment, with previous anti-EGFR therapy and acquired resistance on the most recent anti-EGFR monoclonal antibody therapy (panitumumab or cetuximab) by radiological documentation of disease progression according to RECIST Version 1.1.
3. *MET* amplification detected by a positive liquid biopsy and/or tissue with appropriate regulatory status (collected after disease progression of the previous anti-EGFR therapy).
4. Measurable disease by Investigator in accordance with RECIST Version 1.1.
5. Eastern Cooperative Oncology Group Performance Status (ECOG PS) of 0 or 1.
6. Life expectancy  $> 3$  months.

7. Participants having at least one systemic treatment for mCRC including 1 anti-EGFR monoclonal antibody therapy as the most recent line of therapy for mCRC before study treatment and must have shown a radiologically confirmed by RECIST Version 1.1 complete response (CR) or partial response (PR), both for at least 4 months or stable disease (SD) for at least 6 months to that therapy prior to disease progression.

a. For Cohort A in sites outside of US, participants must only have had one prior systemic treatment for mCRC.

b. For Cohort B in sites in the US only, participants must have had at least two prior systemic treatments for mCRC. First-line treatment must include a fluoropyrimidine and oxaliplatin or irinotecan and second-line treatment must include a fluoropyrimidine, oxaliplatin, or irinotecan.

8. Less than 2 months between the last administration of the most recent EGFR containing regimen and first dosing in this study.

9. Adequate hematological function in the absence of transfusions in 7 days before testing defined by white blood cell count  $\geq 3 \times 10^9/L$  with absolute neutrophil count,  $\geq 1.5 \times 10^9/L$ , platelet count  $\geq 100 \times 10^9/L$ , and hemoglobin  $\geq 8.5 \text{ g/dL}$ .

10. Adequate hepatic function defined by a total bilirubin level  $\leq 1.5 \times$  upper limit of normal (ULN), AST  $\leq 3 \times$  ULN, and ALT  $\leq 3 \times$  ULN. For participants with liver metastases: total bilirubin  $\leq 1.5 \times$  ULN, AST/ALT  $\leq 5 \times$  ULN.

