## 8.9 Immunogenicity Assessments

Whole blood samples of approximately 3.5 mL will be collected for detection of antibodies against cetuximab in serum. Collection times are specified in the SoA (Section 1.3).

The detection of antibodies to cetuximab will be performed using a validated immunoassay method with tiered testing of screening, confirmatory and titration. Confirmed positive antibodies may be further characterized.

CCI

Details on processes for collection and handling of these samples are in a Laboratory Manual. Retention time and possible analyses of samples after the end of study are specified in the respective ICF.

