### **9.2 Sample Size Determination**

The number of participants to be screened is expected to be around 342 participants to account for the described heterogeneity for *MET* amplification in the planned setting (Pietrantonio 2017; Pietrantonio 2015; Raghav 2016; Liu 2019; Mohan 2014; Siravegna 2015; Morelli 2014; Montagut 2018; LC-SCRUM, ASCO 2019 [Nakamura 2019]).

In total, a maximum of 48 participants are planned to be assigned to study intervention such that approximately 22 (Cohort A) and 20 (Cohort B) participants will be treated at RP2D. The 42 participants will be under the same dose level. The sample size calculation of 42 participants is based on the full analysis set (FAS).

The aim is to have 22 participants treated with the RP2D of tepotinib for 2L line treatment (Cohort A) and 20 participants treated with the RP2D for the 3L+ treatment (Cohort B) with at least 6 participants in the safety run-in period, irrespective of cohort.

It is anticipated that 6 eligible participants irrespective of therapy line, will be enrolled into the first part of the study for the determination of RP2D of tepotinib depending on DLTs observed. If 250 mg tepotinib is to be used the number of participants enrolled for the determination of RP2D will increase up to 12 (See Section 9.4.2.1).

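### SAP Table 5 counts any titer rise in a baseline ADA-positive participant as treatment-emergent, so a rise within assay variability can be counted and is pooled with true conversions

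*SAP*

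**What the plan says.** Immunogenicity of cetuximab is a secondary objective (Protocol section 3; SAP section 5). The SAP gives the sampling: "Immunogenicity of cetuximab will be measured by ADA assays at Baseline on Day 1 Cycle 1 and End of Treatment Visit". The Protocol's Schedule of Activities agrees, with ADA samples taken "only on Cycle 1 Day 1 and at EoT".

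SAP Table 5 has two rows for participants who are ADA positive at baseline and have an EoT result:

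- Treatment-emergent negative if the EoT result is "Negative, or positive with titer lower or equal to baseline".
- Treatment-emergent positive if the EoT result is "Positive with titer higher than baseline".

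A baseline-negative participant who is positive at EoT is also labelled treatment-emergent positive. If either sample is missing, the participant is not evaluable. Results are tabulated by cohort and dose level, and listed.

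Protocol section 8.9 requires a validated immunoassay with "tiered testing of screening, confirmatory and titration". Part of that section is redacted. The visible text of the two documents gives no dilution factor, no titer precision and no expected rate of baseline positivity.

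**The concern.** The two baseline-positive rows cover every possible EoT result, so the programmer has no room for a tolerance. On a dilution grid, one step up is enough. With one sample at each end of treatment, no later sample can show whether a small rise persisted.

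The confirmatory tier does not close this gap. It checks that a given sample is truly ADA positive, not that the difference between two positive titers is real.

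Baseline positivity is plausible, though no rate is given. Every participant has progressed on cetuximab or panitumumab (inclusion criterion 2), with less than 2 months between the last dose of that regimen and first dosing in the study (criterion 8).

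What is at stake is how the tabulated count reads. Table 5 gives one label to a participant who developed antibodies on study and to one whose existing titer moved up a step. The count alone cannot show how many positives rest on a small rise.

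**Working it through.** The plan states no ADA figure, so there is nothing of its own to reproduce. The check asks how often Table 5 labels a baseline-positive participant treatment-emergent positive when the true titer has not changed.

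**From the documents:** any rise counts; ties and falls are negative (SAP Table 5); two samples; 42 participants planned at the RP2D, 22 in Cohort A and 20 in Cohort B (Protocol section 9.2).

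**Assumed, because the documents are silent:** independent normal error on the log2 titer with per-sample SD s from 0.15 to 1.0; titers reported on a 2-, 3- or 4-fold grid; both samples remain positive; 5% to 20% of participants positive at baseline; complete sample pairs.

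**Step 1: chance of a reported rise with no true change.** The difference D between the two measured log2 titers is normal with mean 0 and SD s√2. Let g be the grid step in log2 units and let the true titer lie anywhere within a step. Then

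P(any rise) = {E[max(D, 0)] − E[max(D − g, 0)]} / g.

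For s = 0.5 and g = 1 this is 0.282 − 0.025 = 0.257. Simulating 2,000,000 unchanged participants gives the same value. On the 2-fold grid:

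| SD (log2) | Any rise (Table 5) | At least two steps (4-fold) |
|---|---|---|
| 0.15 | 8.4% | 0.0% |
| 0.25 | 14.1% | 0.0% |
| 0.5 | 25.7% | 2.5% |
| 0.75 | 32.6% | 8.6% |
| 1.0 | 36.5% | 14.9% |

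**Step 2: other titer scales.** Over the same range of SD:

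- 3-fold grid: 5.3% to 29.7% for any rise, falling to 0% to 5.5% with a 4-fold minimum.
- 4-fold grid: 4.2% to 25.7% for any rise, unchanged by a 4-fold minimum because a single step is already 4-fold.
- Continuous titers: 50% by symmetry, since ties do not occur.

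**Step 3: expected false cases.** Expected number = 42 × share positive at baseline × false-call probability.

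- 5% positive: 42 × 0.05 = 2.1 people. This gives 2.1 × 0.042 = 0.09 to 2.1 × 0.5 = 1.05.
- 20% positive: 42 × 0.20 = 8.4 people. This gives 8.4 × 0.042 = 0.35 to 8.4 × 0.5 = 4.2.

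The overall range is about 0.1 to 4.2. As a middle case, SD 0.5 on a 2-fold grid with 10% to 20% positive gives 4.2 × 0.257 = 1.1 to 8.4 × 0.257 = 2.2. Because results are shown by cohort, one false case moves a cohort's rate by 1/22 = 4.5 or 1/20 = 5.0 percentage points if every participant is evaluable.

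**The case against.** The strongest reply is that every driver of the size is assumed. With a precise assay and few baseline positives, the expected number is close to zero. Table 5 already treats ties as negative, so on a stepped scale noise must move the result a full step. The rule touches only participants positive at both visits. A low-titer positive that reads negative at EoT is labelled negative, and missing pairs shrink the base below 42. The dilution factor or titer precision may be in the redacted part of Protocol section 8.9 or in the Laboratory Manual. Counting every rise is also a defensible choice if sensitivity is preferred. No test, stopping rule or decision depends on the result. All of this stands, and it limits both size and severity.

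It does not remove the point. Table 5 is unredacted and complete as a rule, and a precision figure held elsewhere would not change how it classifies a one-step rise.

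Three stronger readings are tempting but not supported:

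- **That ADA positives go unconfirmed.** Protocol section 8.9 has a confirmatory tier; what is missing is a second post-baseline sample.
- **That baseline positivity must be common because many participants had cetuximab.** The Protocol allows panitumumab or cetuximab and gives no split.
- **That the error always runs upward.** That holds when titers are unchanged. With true boosts, noise also turns some rises into ties or falls, which are labelled negative.

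**Conclusion.** The point holds as a low-severity clarification. As written, Table 5 can count a titer rise within assay variability as treatment-emergent, and it pools such a case with true conversions.

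A reader might infer that assay noise will create treatment-emergent cases, or take a middle estimate of one or two as a finding. The documents support only that noise can do so. The false-call range of about 8% to 37% rests on an assumed 2-fold grid and SD. The range of 0.1 to 4.2 expected cases also rests on assumed baseline positivity, titer scale and complete pairs. The true number could be zero or several. The endpoint is descriptive, so the consequence is a count that is hard to interpret.

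**What to change.** In SAP Table 5:

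1. For a baseline-positive participant, require an EoT titer at least k-fold above baseline for treatment-emergent positive. Set k before database lock as the smallest fold change that exceeds the titer variability in the assay validation, and state the dilution factor and k in the SAP. Two dilution steps on a 2-fold series is only an illustration; on a 4-fold grid, a 4-fold minimum would change nothing.
2. Change the companion row to negative, or positive with a titer less than k-fold above baseline.
3. Tabulate treatment-induced (negative to positive) and treatment-boosted participants separately.

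The cost is two table cells, one programming condition and a split display, with no new samples. The price is sensitivity: true rises smaller than k-fold are not counted as boosted, and some rises near k will be missed. A k-fold rule also reduces false calls without always removing them: on the 2-fold grid at SD 1.0, a two-step minimum still leaves about 15%.
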